5.1.1.2. Handling of Missing/ Invalid Data

ELISA:

For ELISA binding antibody responses, values below the LLOQ will be imputed with LLOQ/2 EU/mL. For the calculation of fold increases, values of binding antibody responses below the LLOQ will be imputed with LLOQ EU/mL. The LLOQ is provided in the database.

Values above the upper limit of quantification (ULOQ) will be imputed as ULOQ EU/mL. This will be used for the calculation of fold increases. The ULOQ is provided in the database.

5.2. Immunogenicity Against Ad26 Vector

5.2.1. Humoral Immune Response

For immunogenicity against the Ad26 vector, a vector-specific reference value will be defined as the value closest but prior to the administration of the vector. The analysis of the immunogenicity against the vector will be performed only if the assay is available.

Sample interpretation: a sample will be considered positive, if the value is above the assay LLOQ.

The immune response values will be \log_{10} -transformed before any further handling. Results will be presented on the \log_{10} -scale, geometric mean titers and geometric mean increases with corresponding 95% CIS will be provided in the tables.

5.2.1.1. Handling Missing/ Invalid Data

For all outcomes (Ad26) values below the corresponding LLOQ will be imputed with half of the LLOQ (LLOQ/2).

5.3. Analysis

Summary statistics of observed values (on the \log_{10} scale) will be presented for all immunogenicity parameters at each time point (Day 1, 8 and 22). Geometric mean concentrations with corresponding 95% CI and fold increase from pre-booster values will be calculated for ELISA antibody responses (EU/mL) on Day 8 and Day 22.

A linear mixed model with the unstructured variance-covariance and unstructured mean (i.e. including time as a categorical variable) will be used to estimate the geometric mean concentrations and the associated 95% CI at these time points.

Humoral immune response will be graphically presented using regimen profile plots using also data from the parent trial EBL3001.

Reverse cumulative distribution plots will be used to display all the data for each immunogenicity parameter (on the \log_{10} scale) against the percent of participants having at least that level of the parameter. The plots will be used to visually assess a value's rank among all other values and to simplify comparison of immunogenicity parameter distribution by age group.

Percentage of responders will be presented at different time points.

6. SAFETY

No formal statistical testing of safety data is planned. Safety data analysis will be performed on the full analysis set.

Safety data will be analysed descriptively (including 95% CI, if applicable). Baseline for all safety parameters will be defined as the last value before the booster dose.

The safety and tolerability data will include the following:

Solicited local and systemic adverse events (reactogenicity) until 7 days post vaccination.

Unsolicited adverse events, from provision of informed consent onwards until 28 days after booster vaccination.

Serious adverse events (SAEs) until the end of the study (Day 29).

6.1. Adverse events

The analysis of adverse events will be done using the solicited adverse event terms pre-specified in the diary card.

All reported adverse events (solicited local, solicited systemic and unsolicited) after the booster vaccination will be attributed to analysis period as defined in Attachment 1. For each adverse event, the number and percent of subjects who experience at least one occurrence of the given event will be summarized. Summaries, listings, datasets and /or participant narratives may be provided as appropriate, for those participants who die, discontinue study vaccinations due to an adverse event, or experience a severe or serious adverse event.

6.1.1. Definitions

Solicited AEs are precisely defined events (local and systemic) that participants are specifically asked about and which are noted by participants or study staff in the diary. All the other AEs are considered unsolicited. Please refer Clinical Protocol ⁽¹⁾, Section 11 for further details.

Causality

Solicited AEs will be considered as related to the study vaccine. Unsolicited AEs will be considered to be related to the use of the study vaccine if attribution is possibly, probably or very likely. An AE will be considered not related to the use of the study vaccine if the attribution is not related or doubtful. Please refer to Clinical Protocol ⁽¹⁾, Section 11.1.2 for further details.

Severity

The severity of AEs is classified as mild, moderate, severe or potentially life threatening. Please refer to CTP ⁽¹⁾, section 11.1.3 for further details. Solicited events that are graded less than mild, are not considered as AE.

For induration/swelling both the diameter and grading as reported by the investigator are reported in the eCRF. Diameter will be used to derive toxicity grading. The highest grading should be used when both the diameter grading and the investigator-reported grading are available.

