11.1.2 Attribution Definitions

Every effort should be made by the investigator to explain any AE and to assess its potential causal relationship, i.e., to administration of the study intervention or to alternative causes (e.g., natural history of an underlying diseases, concomitant therapies). This applies to all AEs, whether serious or non-serious.

Causality of AEs should be assessed by the investigator based on the following:

Related

There is suspicion that there is a relationship between study intervention and AE (without determining the extent of that probability); there is a reasonable possibility that the study intervention contributed to the AE.

All AEs assessed as possibly, probably or definitely related to the study intervention will be considered related to the study intervention.

Unrelated

There is no suspicion that there is a relationship between the study intervention and the AE; there are other more likely causes and administration of the study intervention is not suspected to have contributed to the AE.

All AE assessed as unrelated or doubtfully related to the study intervention will be considered unrelated to the study intervention.

By definition, all solicited AEs at the injection site (local) will be considered related to the study intervention administration.

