6.1.2. Imputation

Missing data will not be imputed. If relationship of AEs to the study vaccine could not be derived (i.e. missing or unknown) it will be considered as unknown, for analysis purposes. Solicited local AEs will be considered as related with the use of study vaccine. Missing relationships will not be imputed.

Period allocation of AEs is defined in Attachment 1.

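### SAP 6.1.1 treats every solicited AE, systemic as well as local, as vaccine-related, against protocol 11.1.2, SAP 6.1.2 and a later sentence in its own paragraph

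*SAP*

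**What the plan says.** SAP 6.1.1 sets the scope of the term first: "Solicited AEs are precisely defined events (local and systemic) that participants are specifically asked about". Its causality paragraph then has three rules and a pointer.

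- Sentence 1: "Solicited AEs will be considered as related to the study vaccine", with no limit to local events.
- Sentence 2 gives the attribution categories that make an AE related, but for unsolicited AEs only.
- Sentence 3 says that an AE, with no qualifier, is not related when its attribution is doubtful or not related.
- The paragraph closes by sending the reader to the protocol: "Section 11.1.2 for further details".

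Protocol 11.1.2 asks the investigator to assess causality for every AE. On ratings at the lower end it says: "All AE assessed as unrelated or doubtfully related to the study intervention will be considered unrelated to the study intervention". Its one automatic rule is: "By definition, all solicited AEs at the injection site (local) will be considered related to the study intervention administration".

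SAP 6.1.2 agrees with the protocol: "Solicited local AEs will be considered as related with the use of study vaccine". For an AE whose relationship is missing or unknown it says "it will be considered as unknown, for analysis purposes", and adds: "Missing relationships will not be imputed".

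SAP 6.1.3 plans relatedness tables for solicited and unsolicited AEs alike. SAP section 3 states that the analysis planned in the protocol is unchanged.

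**The concern.** Safety and tolerability form a primary objective, and the relatedness tables are part of how it will be reported. The SAP gives more than one answer for the same event. A headache rated doubtful is related under the first sentence of the 6.1.1 paragraph and not related under the third. A fever with no recorded relatedness is related under 6.1.1 and unknown under 6.1.2. Two programmers working from the same SAP could produce different tables, and one of those tables would depart from the protocol without the departure being declared.

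**Working it through.** The plan states no figure on this point, so the check compares the rules case by case and then works out what one reclassified child does to a table row.

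**Step 1. Classify each type of solicited AE under each rule.**

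| Solicited AE | SAP 6.1.1, sentence 1 | SAP 6.1.1, sentence 3 | Protocol 11.1.2 | SAP 6.1.2 |
|---|---|---|---|---|
| Local, rated possible or probable | related | does not apply | related | related |
| Local, rated doubtful or not related | related | not related, if read literally | related | related |
| Systemic, rated possible or probable | related | does not apply | related | no rule |
| Systemic, rated doubtful or not related | related | not related | unrelated | no rule |
| Systemic, relatedness missing | related | does not apply | no rule | unknown |

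The first sentence of 6.1.1 departs from the protocol in the fourth row and from 6.1.2 in the fifth. The third sentence, read literally, departs from the protocol in the second row, so it needs an exception for solicited local AEs.

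There is also a gap. The second sentence covers unsolicited AEs only. If sentence 1 is cut back to local events and nothing else changes, 6.1.1 has no sentence by which a solicited systemic AE rated probable becomes related.

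**Step 2. Direction.** Sentence 1 can move a solicited systemic AE from unrelated or unknown to related. It can never move one the other way. Solicited local AEs are related under sentence 1, protocol 11.1.2 and SAP 6.1.2, and unsolicited AEs are outside sentence 1.

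**Step 3. Size per child.** SAP 6.1.3 counts participants with at least one event. SAP 1.4 gives n of about 25 per age group. If k children change category in a row, that row rises by k/n:

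- k = 1: 1/25 = 4.0 percentage points
- k = 3: 3/25 = 12.0 percentage points
- k = 5: 5/25 = 20.0 percentage points

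These values of k are assumptions that show a range. The documents give no rate of doubtful, not-related or missing ratings. A child counts towards k only if none of that child's events in the row is rated related.

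**Step 4. What one child does to a reported row.** SAP section 2 specifies exact Clopper-Pearson intervals. For 0/25 the upper limit is 1 − 0.025^(1/25) = 0.137, so the row reads 0% (0 to 13.7%). For 1/25 it reads 4.0% (0.1 to 20.4%). The zero starting point is only an example. The intervals describe sampling uncertainty and do not measure the misclassification.

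**The case against.** The strongest defence is that the intention can be recovered. Sentence 3 matches the protocol for a doubtful systemic event, the paragraph points to 11.1.2, and 6.1.2 names solicited local AEs and keeps missing relatedness as unknown. SAP Attachment 3 handles relatedness of solicited events as recorded data: it refers to diary relatedness for temperature and shows relatedness in a headache example. Most likely the word local was dropped. This stands as a reading of intent. It does not make the paragraph safe to program from, because sentence 1 is unqualified, comes straight after a definition that includes systemic events, and is followed by a sentence limited to unsolicited AEs.

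It can also be said that neither protocol 11.1.2 nor SAP 6.1.2 uses the word only. That is true. The restriction is inferred from the qualifier in both places and from the protocol's requirement that causality be assessed for all AEs.

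A reader might infer more than the documents support:

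- **That the related table for solicited systemic AEs will simply repeat the all-events table.** This holds only if sentence 1 overrides sentence 3 and 6.1.2. The text does not settle which prevails.
- **That a safety signal could be hidden.** It could not, since the related count can only rise. Incidence and severity summaries do not use this rule, and the pausing rules in protocol 8.3.2 act on events during the study and not on this derivation.
- **That Attachment 3 proves relatedness is collected for every systemic item.** It is a record-conversion rule that applies where relatedness is collected, and its headache ends as Probable, which is related under either rule.

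**Conclusion.** The conflict is real and limited. As written, the first sentence of the 6.1.1 causality paragraph contradicts protocol 11.1.2, SAP 6.1.2 and the third sentence of the same paragraph, and SAP section 3 declares no departure. If that sentence governs the programming, solicited systemic AEs rated doubtful or not related, or with missing relatedness, are overcounted as related. The effect is confined to the relatedness split of solicited systemic AEs, goes upward only, and is 4 percentage points per reclassified child in an age group of 25. The total cannot be derived from the documents.

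The textual conflict is certain. The effect on the tables rests on two things not visible here: which sentence the programmer follows, and whether the CRF records relatedness for solicited systemic items.

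**What to change.** First check whether the CRF records relatedness for the solicited systemic items. Protocol 11.3.1 already requires the investigator's opinion on relationship for AEs, so no new data collection should be needed if those pages follow it.

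If relatedness is recorded:

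1. Replace the first two sentences of the 6.1.1 causality paragraph with: *Solicited local AEs are related by definition. Solicited systemic and unsolicited AEs are related if the recorded attribution is possible, probable or [top category].*
2. Use one term for the top category. The SAP now says very likely where protocol 11.1.2 says definitely.
3. Keep the sentence on doubtful and not-related attribution, and apply it to all AEs except solicited local AEs.
4. Leave 6.1.2 as it is, so that missing relatedness of other AEs stays unknown.

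If relatedness is not recorded for these items, or the sponsor intends the broad rule, declare it in SAP section 3 as a change from protocol 11.1.2, and align 6.1.2 and the sentence on doubtful and not-related attribution with it.

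Either route costs a few lines of SAP text and a CRF check. It should be settled before the relatedness tables are programmed.

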6.1.1.1. Solicited Local (Injection Site) Reactions

The analysis of solicited AEs will include:

- Erythema (redness of skin)
- Swelling/ Induration
- Pain/Tenderness
- Itching at the injection site

6.1.1.2. Solicited Systemic Adverse Events

The analysis of systemic solicited adverse events will include:

- Fatigue/tiredness
- Headache
- Nausea/vomiting
- Myalgia (muscle pain)
- Arthralgia (joint pain)
- Fever (defined as body temperature of 38⁰ or higher)

Adverse Events of Special Interest

AESIs (including potential AESIs) are significant AEs that are judged to be of special interest because of clinical importance, known or suspected effects of similar vaccines, or based on nonclinical signals.

- Thrombosis with Thrombocytopenia Syndrome (TTS)
- Thrombotic events: suspected deep vessel venous or arterial thrombotic events as detailed in Appendix 2

and/or

- Symptomatic thrombocytopenia, defined as platelet count below LLN for the testing lab

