After vaccination, participants will remain under observation at the study site for at least 30 minutes for surveillance for any acute reactions, or longer if deemed necessary by the investigator. Symptoms of solicited local and systemic AEs will be collected in the diary in the evening after the vaccination and then daily for the next 7 days. Diaries will be completed at home by either a project field worker who will visit the participant during daily visits or by the parent/guardian and checked by a project field worker for 6 days. Day 8 of the diary will be completed by study site staff at the clinic. Diary information will be transcribed by the study personnel in the diary CRF pages. Once a solicited symptom from a diary is considered to be of severity Grade 1 or above, it will be referred to as a solicited AE.

Solicited Injection Site (Local) Adverse Events

Parents/guardians (or the project field worker) will be asked to note in the diary occurrences of tenderness, erythema and swelling at the study intervention injection site daily for 6 days post-vaccination (day of vaccination and the subsequent 6 days). The extent (largest diameter) of any erythema and swelling should be measured (using the ruler supplied) and recorded daily. Day 8 of the diary will be completed by study staff at the site clinic.

- Injection Site Tenderness**

Injection site tenderness is a painful sensation localized at the injection site upon palpation or movement of the limb. Due to the subjective nature of the reaction, the severity assessment of tenderness is self-reported (if a participant is unable to provide self-report, other reporters include parent/care giver or health care provider).

- Injection Site Erythema**

Injection site erythema is a redness of the skin caused by dilatation and congestion of the capillaries localized at the injection site. It can best be described by looking and measuring.

- Injection Site Swelling**

Injection site swelling is a visible enlargement of the site of injection. It may be either soft (typically) or firm (less typical).

Note: Any other injection site events not meeting the above case definitions should be reported separately as unsolicited AEs.

Solicited Systemic Adverse Events

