Parents/guardians will be instructed on how to record daily temperature using a thermometer provided for home use. The axillary temperature of the participant should be recorded in the diary in the evening of the day of vaccination, and then daily for the next 6 days at approximately the same time each day. The participant's temperature on Day 8 will be taken by study staff at the site clinic. If more than one measurement is made on any given day, the highest temperature of that day will be used in the CRF.

In this protocol, fever is defined as an endogenous elevation of body temperature $\geq 38^{\circ}\text{C}$, as recorded in at least one measurement.

Parents/guardians will also be instructed on how to note daily in the diary symptoms for 6 days post-vaccination (day of vaccination and the subsequent 6 days) any of the following events:

- body temperature
- fatigue/malaise
- chills
- headache
- nausea/vomiting
- muscle pain
- joint pain
- loss of appetite, in young children

Symptoms 7 days post vaccination (Day 8) will be assessed and recorded by study staff at the site clinic.

Physical Examination

A full physical examination will be performed at the screening visit. At subsequent study visits a brief, symptom-directed examination will be performed based on any clinically relevant issues, clinically relevant symptoms and medical history. The symptom-directed physical examination may be repeated if deemed necessary by the investigator. Physical examinations will be performed by the investigator or by a designated medically-trained clinician. Physical examination findings (i.e. abnormalities) prior to vaccination (Day 1) are to be recorded as medical history, but after vaccination as an AE.

Vital Signs

Axillary temperature, blood pressure, pulse/heart rate (beats per minute), and respiratory rate (breaths per minute) will be assessed.

Blood pressure and pulse/heart rate measurements will be assessed with a completely automated device. Manual techniques will be used only if an automated device is not available. Pulse/heart rate measurements should be preceded by at least 5 minutes of rest in a quiet setting without distractions.

Clinical Laboratory Tests

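### The SAP's solicited adverse event lists omit chills and loss of appetite and add injection-site itching, relative to protocol 8.3.1, without declaring a change

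*SAP*

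**What the plan says.** **Protocol 8.3.1, local.** Parents or field workers "will be asked to note in the diary occurrences of tenderness, erythema and swelling at the study intervention injection site daily". For anything else at the injection site the rule is explicit: "Any other injection site events not meeting the above case definitions should be reported separately as unsolicited AEs".

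**Protocol 8.3.1, systemic.** Parents "will also be instructed on how to note daily in the diary symptoms" from a list of eight items: body temperature, fatigue/malaise, chills, headache, nausea/vomiting, muscle pain, joint pain, and "loss of appetite, in young children".

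**SAP lists.** Section 6.1.1.1 names four local terms: erythema, swelling/induration, pain/tenderness and "Itching at the injection site". Section 6.1.1.2 opens with "The analysis of systemic solicited adverse events will include" and names six: fatigue, headache, nausea/vomiting, myalgia, arthralgia and fever.

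**SAP general rule.** Section 6.1 states: "The analysis of adverse events will be done using the solicited adverse event terms pre-specified in the diary card". Section 6.1.1 defines solicited AEs as events "that participants are specifically asked about and which are noted by participants or study staff in the diary" and treats the rest as unsolicited. Attachment 3 builds the solicited dataset from the whole diary plus on-site assessments.

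**Declared changes.** SAP section 3 reports none. The SAP introduction ties it to protocol version 2.0 of 15 June 2021, the version reviewed here, so the difference is not left over from an amendment.

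**The concern.** Safety and tolerability is a primary objective, and whether an event is solicited or unsolicited decides how it is reported. Under SAP 6.1.3, solicited AEs are summarised by local and systemic class and also get duration and time-to-onset summaries; unsolicited AEs are summarised by system organ class and preferred term. Under SAP 6.1.2 and protocol 11.1.2, solicited local AEs are related by definition, whereas an unsolicited AE takes the investigator's attribution.

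Protocol 1.2.3 names chills, loss of appetite in young children and local itching among the vaccination risks to be monitored. Protocol 1.1 reports decreased appetite as the most frequent solicited systemic event in the 1–3 years cohort of the earlier paediatric studies. Two of the three mismatched items are therefore ones the protocol meant to ask about actively, and the third is one it did not list as solicited.

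**Working it through.** There is no planned figure to reproduce: the sample is one of convenience and no solicited event rates are given. The check is an item-by-item comparison of protocol 8.3.1 with SAP 6.1.1.1 and 6.1.1.2. Near-synonyms are counted as matches (malaise with tiredness, body temperature with fever, tenderness with pain/tenderness, swelling with swelling/induration), so wording does not inflate the count.

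| Class | Protocol 8.3.1 | SAP | Shared | Protocol only | SAP only |
|---|---|---|---|---|---|
| Local | 3 | 4 | 3 | none | itching |
| Systemic | 8 | 6 | 6 | chills, loss of appetite | none |
| Total | 3 + 8 = 11 | 4 + 6 = 10 | 3 + 6 = 9 | 2 | 1 |

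Distinct items: 11 + 10 − 9 = 12, of which 2 + 1 = 3 differ. Missing systemic items are 2 of 8 for a child asked about appetite and 1 of 7 for a child not asked. Protocol 8.3.1 gives no age cut-off for that item, so the documents do not show how many children fall on each side.

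**What the mismatch means for each possible diary card**

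- *Card as in protocol 8.3.1.* The rule in SAP 6.1, 6.1.1 and Attachment 3 makes chills and loss of appetite solicited and itching unsolicited. The SAP lists, read as exhaustive, say the reverse. The SAP then conflicts with itself.
- *Card as in the SAP lists.* The SAP is consistent, but collection departs from protocol 8.3.1.
- *Some other mix, for example all 12 items.* The SAP lists would then omit items that the card solicits, or the card would depart from the protocol, or both.

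The two sets of lists differ, so no card can match both. At least one document needs correction in every case, but which one cannot be settled without the card.

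**Size.** Let *k* be the number of children in a group of *n* whose only solicited systemic event is chills or loss of appetite. Leaving those items out lowers the percentage with any solicited systemic AE by *k*/*n*. With about 25 per age group (SAP 1.2):

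- *k* = 0: no change
- *k* = 1, *n* = 25: 1/25 = 4.0 points
- *k* = 1, *n* = 50: 1/50 = 2.0 points

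The documents give nothing from which to estimate *k*.

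**The case against.** The best defence is that the SAP lists need not be exhaustive: both are introduced as what the analysis will include. The general rules then do the work. SAP 6.1 points to the diary card, 6.1.1 defines solicited by what was asked, and Attachment 3 takes in the whole diary. Protocol 10.4 also puts diary information into the analysis. Read together, chills or loss of appetite recorded in the diary would be analysed as solicited, and the lists are merely incomplete. There is no hypothesis test, and no pausing rule in protocol 8.3.2 counts solicited events.

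Much of this stands for the two omissions. It does not explain itching, which is a positive addition that protocol 8.3.1 would class as unsolicited. Open-ended lists would also leave the contents of the solicited tables to be worked out from other sections.

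Three stronger readings are tempting, and the documents support none of them.

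- *Events would be lost.* Unsolicited AEs are tabulated too, so classification is at stake, not reporting as such.
- *Itching would automatically be counted as related.* That follows only if it is analysed as solicited. If the card does not ask about it, SAP 6.1.1 makes a spontaneous report unsolicited, with the investigator's attribution. Nor can automatic relatedness be extended to systemic items: one sentence in SAP 6.1.1 covers all solicited AEs, but SAP 6.1.2 and protocol 11.1.2 confine it to local ones, and Attachment 3 uses collected relatedness for headache.
- *The commonest reaction in the youngest group would be hidden.* The result in protocol 1.1 concerned children aged 1–3 when vaccinated. Here they are more than two years past that regimen, and no rate is given to carry over.

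**Conclusion.** The concern holds as an undeclared mismatch between the SAP lists and protocol 8.3.1: three of 12 distinct items differ. That part rests only on the two texts.

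The conflict with the SAP's own diary-card rule is conditional on the card following protocol 8.3.1. A reader might infer that the SAP certainly contradicts itself; without the card this cannot be said. On that condition, and reading the lists as exhaustive, chills and loss of appetite would be left out of the solicited systemic class total and the duration and onset summaries.

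No numerical impact is demonstrated; it may be zero. It should still be corrected before the tables are programmed, because it concerns a primary objective and costs little to put right.

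**What to change.** 1. Amend SAP 6.1.1.1 and 6.1.1.2 to list the items of protocol 8.3.1, adding chills and loss of appetite to the systemic list.
2. Tabulate injection-site itching as unsolicited unless the card solicits it.
3. Base the loss-of-appetite percentage on the children in whom it was solicited according to the card or CRF, and state that age range, since the protocol gives none.
4. Check the final lists against the card. Declare any analysis difference that is kept in SAP section 3. A difference in what was collected is not cured by a SAP note; handle it as a departure from, or an amendment to, the protocol (protocol 16.1).

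The cost is SAP wording, a few table rows and one check of the card. If the card follows protocol 8.3.1, no new data are needed. The downside is that reported solicited reactogenicity may be slightly higher, and loss of appetite will have a smaller denominator than the other items.
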